11.0 APPENDICES

Appendix A: Physician Patient-Specific Recruitment Letter

Helping Oncology Patients Explore- Genomics (HOPE- Genomics) Web Tool Randomized Clinical Trial

[DATE]

Dear Dr. [PHYSICIAN LAST NAME],

We are writing to you because your patient, [PATIENT NAME, MRN], is eligible for participation in the HOPE-Genomics research study involving a web-based, patient-facing genomic education tool.

Please let us know if this is incorrect, or if you do not feel that this patient would be a good fit for our research study. We plan to otherwise approach your patient at a future clinic appointment or via email/mail/phone if we do not hear back from you over the next 24 hours. Please refer to the bottom of this email for the eligibility criteria of this study.

IF YOU DO NOT WISH FOR US TO CONTACT THIS PATIENT, PLEASE LET US KNOW. We will otherwise proceed with approaching him/her.

Note: If your patient enrolls in the study, your patient will have access to the HOPE-Genomics tool with HIS/HER genomic test results approximately 3 days after the results become available in EPIC.

For more information or questions about the study please contact the study Principal Investigator, [name], AM, or the Clinical Research Coordinator, [name] at [contact].

We look forward to hearing from you!

Thanks so much,

The HOPE-Genomics Team

[name], [name], [name], [name], and [name]

Division of Clinical Cancer Genomics

Medical Oncology and Therapeutics Research

Department of Population Sciences

City of Hope Comprehensive Cancer Center
[name]
[name]

[INSERT PATIENT NAME] is eligible because [HE/SHE]:

- Is receiving somatic, germline or paired somatic/germline sequencing through COH IRB 07047
- Has a cancer diagnosis
- Has an ECOG performance status of 0-2, and
- Is fluent in English

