4.0 STUDY PROCEDURES

4.1. Informed Consent and Baseline Survey

Potentially eligible patients will be approached by study team members for verbal informed consent, either by mail/ email, during clinic visits, or by phone. Patients will receive a study packet that will contain an invitation letter, interest postcard, return envelope, and informed consent document. Patients will be randomized into one of three arms immediately after enrollment. Arm 1 is usual care, Arm 2 is return of results only in the HOPE-Genomics tool, and Arm 3 is return of results plus pretest education in the HOPE-Genomics tool.

Arm 1 patients will receive

a pamphlet (20430 Educational Brochure in iRIS) about WES after they enroll. Their clinician will return their genomics test results in a typical manner, without the assistance of the HOPE-Genomics tool.

Arm 2 patients will receive their genomics test results both from their clinician and from the HOPE-Genomics tool but will only view the tool after their results are available. Arm 3 patients will view the HOPE-Genomics tool (containing educational content) before their sequencing results are available. These patients will also receive their genomics test results both from their clinician and from the HOPE-Genomics tool. After completing all study surveys at 9 months post results disclosure, participants in Arm 1 (usual care), will receive access to the HOPE-Genomics tool, which will contain both the educational information and the personalized genomics results.

Table 1: Outcome and covariate data collection

			Patient surveys			MRA
	Baseline	Pre-edu. survey	T1	T2	T3	
Genetic Care outcomes						
MD recommendations						
Screening, surgery, meds			X	X	X	X
Referrals GC, specialists			X	X	X	X
Cascade testing			X	X	X	X
Patient utilization/behavior						
Screening, surgery, meds			X	X	X	X
Consult GC, specialists			X	X	X	X
Inform family members			X	X	X	
Cascade testing			X	X	X	
Patient-centered outcomes						
Recall of results	X		X	X	X	X
Understanding of results			X	X	X	
Genomic knowledge	X	X	X	X		
Engagement in care			X	X	X	
Information seeking				X		
Psychosocial impact	X		X	X	X	
Follow up outcomes						
HOPE-Genomics usability			X	X		
Satisfaction with MD-patient communication and care			X	X		
Covariates						
Socio-demographics	X					X
Clinical information						X
Other (e.g., health literacy)	X					X

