4.3 Tool Access and Patient Pre-Education Survey

After enrollment, all participants will be provided with a hard-copy or electronic educational pamphlet about whole-exome sequencing (WES). Patients in the Return of Results plus Pre-test Education arm will be provided with login and dual-factor authentication instructions and have immediate access to educational content in the tool, with their sequencing results to become available in the tool shortly after their results are available in Epic. Patients in the Return of Results Only arm will not be able to see tool content until their genomic test results are available (e.g., ~2-6 weeks after sample collection). Patients in the Usual Care arm will have access to the tool content after completing all study surveys, approximately ~9 months after their sequencing results are available.

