4.4 Results Disclosure

We expect results to be available within ~3-14 days of sample acquisition. We will monitor the patients' laboratory data to see when results have been finalized. Lab results and variant interpretations for the HOPE Genomics intervention will be stored in a custom genomic database designed by COH Research Informatics. All results will be validated by study staff before data are input into the HOPE-Genomics tool. All clinicians will receive results through the EHR. Additionally, clinicians with patients in the intervention arm will also be able to view their patients' results through the HOPE-Genomics after individual-level patient data have been entered into HOPE-Genomics. Results will be available to patients in the HOPE-Genomics app approximately 3-14 days after they are available in the EHR.

At this time, we will ask patients in the Return of Results Only intervention arm, (Arm 2) and the Return of Results + Pre-Test Education arm (Arm 3) to log into the HOPE-Genomics tool on their own time. Study staff will provide patients with instructions to create an account and log into the tool using dual-factor authentication. Study staff will track patients' tool access through Google Analytics and call or send automated RedCap reminders to encourage tool use, if necessary. Study staff will track patients' tool access through Google Analytics and call and/or send automated REDCap reminders to encourage tool use, if necessary. In addition, the study staff will be available to help patients access HOPE-Genomics at subsequent clinic/infusion visits or via secure web conference at any point in time following the disclosure of their test results until the end of the study (with coordination with the study team).

Patients in the control arm (Arm 1) will have their results returned in clinic by their provider, with no changes to the clinician's typical delivery method. Patients will be provided an educational pamphlet that generally describes sequencing and will granted access to the HOPE-Genomics tool with their results after completing all follow-up study surveys, approximately 9 months after their results are in the EHR.

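### The recruitment letter to treating physicians promises tool access about 3 days after results for any patient who enrolls; this is untrue for the Usual Care third and could alter how control-arm results are delivered.

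*Combined protocol and SAP*

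**What the plan says.** **The letter.** Appendix A is addressed to the physician of a named patient. Its note says that, if the patient enrolls, "your patient will have access to the HOPE-Genomics tool with HIS/HER genomic test results approximately 3 days after the results become available in EPIC". It is sent before any contact about the study: "We plan to otherwise approach your patient at a future clinic appointment or via email/mail/phone if we do not hear back from you" within a day. The heading calls the study a randomized clinical trial. The body mentions neither the three arms nor delayed access in one of them.

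**The protocol body.** Section 4.1 places allocation later: "Patients will be randomized into one of three arms immediately after enrollment". For Arm 1 it says: "Their clinician will return their genomics test results in a typical manner, without the assistance of the HOPE-Genomics tool". Section 4.3 adds: "Patients in the Usual Care arm will have access to the tool content after completing all study surveys", at roughly 9 months. Section 4.4 gives the same timing, "approximately 9 months after their results are in the EHR", and says that control patients "will have their results returned in clinic by their provider, with no changes to the" clinician's usual way of doing it. For the intervention arms, Section 4.4 has results appearing in the tool "approximately 3-14 days after they are available in the EHR".

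**The endpoint.** Sections 6.0 and 6.2.1 set the primary outcome as recall of personal genomic results at 10 days after disclosure, comparing Usual Care with Arms 2 and 3 pooled.

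**The concern.** In this trial the comparator is not a pill or a fixed script. It is whatever the treating clinician ordinarily does when returning genomic results. The letter goes to that same clinician and misdescribes what a Usual Care patient will receive.

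A clinician who believes that the patient will see results in an educational tool within days might change the length, content or timing of the disclosure conversation. If that happened in Usual Care, the control group would no longer represent unchanged practice, and the primary comparison would be against a somewhat different condition from the one in Section 4.4. Recall is measured about 10 days after disclosure, so that conversation is the main source of what a control patient can recall.

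**Working it through.** The point is mainly textual, so the passages come first and the arithmetic is short.

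**1. Access to the tool with results, by source**

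| Patient | Appendix A | Sections 4.1, 4.3, 4.4 |
|---|---|---|
| Usual Care (Arm 1) | about 3 days after results are in EPIC | after all surveys, about 9 months after results |
| Return of results (Arm 2) | about 3 days | about 3-14 days |
| Return of results plus pretest education (Arm 3) | about 3 days | about 3-14 days (educational content earlier) |

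The Usual Care row is a contradiction. In the other two rows the letter gives the lower end of the protocol's range as if it were the expected time. That is a lesser mismatch.

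**2. Who receives the statement.** The letter precedes the approach to the patient, the approach precedes enrollment, and randomization follows enrollment. The letter therefore cannot be tailored to arm, and by design it covers patients later allocated to any of the three.

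**3. Share affected.** Section 6.1 plans 155 patients per arm and 465 in total: 155/465 = 0.333. This is the allocation share for which the statement is untrue. It does not measure harm.

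**4. The plan's own figure.** Inputs from Section 6.2.1: p1 = 0.39, n1 = 130; p2 = 0.54, n2 = 260; two-sided alpha 0.05. With the pooled-variance normal approximation,

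power = Φ{ [ (p2 − p1) − 1.96·√(p̄(1−p̄)(1/n1 + 1/n2)) ] / √(p1(1−p1)/n1 + p2(1−p2)/n2) }

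- p̄ = (130 × 0.39 + 260 × 0.54)/390 = 0.49
- null SE = √(0.2499 × 0.01154) = 0.0537, times 1.96 = 0.1052
- alternative SE = √(0.2379/130 + 0.2484/260) = 0.0528
- power = Φ[(0.15 − 0.1052)/0.0528] = Φ(0.848) = 0.80

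The stated 80% is reproduced. No corrected figure follows from the letter, because nothing in the documents says how far, or which way, clinician behavior would move.

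**5. Illustration only.** Assume that Arm 1 recall shifts by an amount chosen here and that Arms 2 and 3 do not shift at all. The same formula gives:

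| Arm 1 recall | Arms 2/3 recall | Chance of a significant result favoring the tool |
|---|---|---|
| 44% | 54% | 0.46 |
| 42% | 54% | 0.61 |
| 39% (plan) | 54% | 0.80 |
| 36% | 54% | 0.92 |
| 34% | 54% | 0.97 |
| 36% | 39% (no tool effect) | 0.08, against 0.025 with no shift |
| 34% | 39% (no tool effect) | 0.16, against 0.025 with no shift |

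The table shows that the comparison is sensitive to the control rate in both directions. It does not estimate what the letter does. If all arms shifted by the same number of points, the difference in proportions would be unchanged.

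**The case against.** The strongest reply is that a loosely worded letter is a long way from a biased comparison. Several parts of that reply stand.

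- **All arms get the same sentence.** Any effect on clinicians could occur in Arms 2 and 3 as well. A reader might infer that a shift of 3-5 points in Usual Care recall would put the 15-point contrast out by 3-5 points, a fifth to a third of the effect. The documents do not support that: the shift has no source, and the inference requires that only Arm 1 moves.
- **Direction is unknown.** Explaining less would tend to lower control recall; disclosing sooner could act either way. A flat statement that the primary comparison is biased goes too far.
- **The letter does not say that the tool replaces the clinician.** It describes a patient-facing educational tool, and under Section 4.1 clinicians return results in every arm. A reader might infer that some patients could be left with no explanation from anyone. Nothing in the letter invites a clinician to skip disclosure.
- **Clinicians may learn the arm later.** Section 4.4 lets clinicians of intervention patients see results in the tool, and the letter offers a contact for questions. The text available describes no notice of Usual Care assignment, but some appendix pages were removed, so one may exist.

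One part does not stand. The words in the heading that identify a randomized trial do not correct an unconditional note, because a physician could take randomization to concern content or timing while still expecting access for everyone. A later notice would lessen any effect, but the letter would still be untrue as written.

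**Conclusion.** The concern holds as an inconsistency with a plausible route to the primary endpoint. The letter's statement is untrue for the planned Usual Care third, and for the intervention arms it gives only the lower end of the protocol's window. The misstatement reaches the person who delivers the control condition, so it could alter that delivery, which makes it more than clerical. The design in Sections 4.1, 4.3 and 4.4 is itself clear; only the letter departs from it.

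This rests on two assumptions: that the letter is used as its place in the recruitment sequence implies, and that no later communication corrects it before results are disclosed. The second cannot be checked from the text available. The size and direction of any effect on recall are unknown, and none is claimed. It should be corrected, and it does not call into question the sample size or the planned analysis.

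**What to change.** Reconcile Appendix A with Sections 4.1, 4.3 and 4.4. Replace the note with wording that says:

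- patients who enroll are randomized to one of three arms;
- access to the tool, and its timing, depend on the arm;
- about one third of patients will not have the tool until after the 9-month survey;
- for Usual Care patients, results are returned in the clinician's typical manner, as Section 4.4 already provides;
- in the intervention arms, results appear in the tool about 3-14 days after they are in the EHR.

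The fourth item should be confined to Usual Care. Section 4.4 requires unchanged delivery only there, and extending it to every patient would be a new instruction about Arms 2 and 3.

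The cost is a minor wording amendment, with no change to procedures, sample size or analysis. It applies only to letters sent from then on. Appendix U addresses participants who had already consented, so some letters may already have gone out, and new wording cannot undo those.

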Appendix E: Patient Interest Postcard

Front of postcard:

Back of postcard:

Study ID: _____

If you are not interested in participating, please check off the box below and mail this postcard back. Thank you!

I have received and reviewed the information related to the HOPE study.

- I am interested in participating. Please contact me to discuss the study.
- I am not interested in participating. Please remove my name from the contact list.

Appendix G: Patient Script to Setup Access to HOPE-Genomics tool – RoR + Intervention Arm

Dear [PATIENT NAME],

This is the HOPE-Genomics Team from City of Hope. You may remember speaking with [consenter] about your participation in the HOPE-Genomics study, involving a web-based education tool for patients with genetic testing at City of Hope. Thank you for completing your first survey for the study!

At this time, we would like to invite you to log into and view the HOPE-Genomics before your results are ready. The tool contains helpful information, including a video, that explains the details of genomic testing and its implications for your health. You may log into the tool by clicking the following link: <https://hopegenomics.coh.org/login>.

Once you have viewed the tool, we will send you a follow-up survey. We have also attached instructions on how to access the tool.

If you have any problems accessing the tool, we can accommodate in-person visits at City of Hope Duarte campus or remote visits using web conferencing (i.e. Zoom). Please call [INSERT CRA's PHONE NUMBER] or email us at [contact] if you would like to schedule an appointment to speak with study staff.

If you have any additional questions about this research study, please call the Principal Investigator, [name] at [contact] or the Clinical Research Coordinator, [name] at [contact]. You can also reach the Institutional Review Board at City of Hope by calling [contact].

Thank you for all your help with our research at City of Hope, and we look forward to hearing from you!

The HOPE-Genomics Team

[name], [name], [name], [name], and [name]

Division of Clinical Cancer Genomics

Medical Oncology and Therapeutics Research

Department of Population Sciences

City of Hope Comprehensive Cancer Center

[name]

[name]

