Approximately 2-3 days after completing the baseline survey, patients in all study arms will complete a pre-test education survey that assesses general genomic knowledge prior to results disclosure. For patients requesting paper versions of the baseline and pre-test surveys, we will mail the pre-test survey 1 week after mailing the baseline. This will ensure that patients who opt for paper surveys can complete the pre-test survey within 2-3 days of completing their baseline survey. As with all study surveys, patients will also have the option of completing the pre-test education survey over a scheduled phone or Zoom call with a study staff member. During the phone or Zoom call, study staff will not assist patients in selecting the correct answers for questions pertaining to their understanding of cancer and genetics. As mentioned above, patients in the Return of Results plus Pre-test Education arm (Arm 3) will view the HOPE-Genomics tool prior to their results disclosure and completion of this survey. The HOPE-Genomics tool will be populated with educational material about genomics, cancer, and other related content, but without the patient's individual test results. We will track Arm 3 patients' tool access through Google Analytics, which is an IT-approved software that monitors user interaction metrics within the HOPE-Genomics platform, specifically button clicks per page, page scrolls, double clicks, and page-viewing duration times. We are utilizing Google Analytics to better understand which features of the tool are most frequently used by patients and identify technical aspects of the tool that need improvement. The version of Google Analytic implemented (GA4) in the HOPE-Genomics platform has a process of data anonymization, so no IP address or other PHI is collected from the participants. In addition, Google Analytics does not gather text data from the HOPE-Genomics platform and therefore has no access to potential PHI within the HOPE-Genomics platform. Additional security features of the HOPE-Genomics platform are discussed in Section 4.2 of this protocol (HOPE-Genomics Tool Details & Security Features). Study staff will call and/or email patients in the Return of Results plus Pre-Test Education arm within approximately 24 hours of receiving their login information to track whether patients interact with the HOPE-Genomics platform and if patients have not accessed the tool, study staff will encourage and facilitate intervention use. All other patients (Usual Care & Return of Results Only) will only view the WES pamphlet before completing this survey. The HOPE-Genomics educational content will be available to those patients in the Return of Results Only and Usual Care arms but will only be made available after their genomic test results are available in the tool.

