Test-related distress: We hypothesize that patients who view HOPE-Genomics will have lower test-related distress than patients in the usual care group: Patients will be assessed at 3 post-disclosure time points (T1-T3) using the PAGIS Certainty Scale and the FACToR. Some patients may have little test-related distress, whereas others may score higher (e.g., if testing reveals cancer or non-cancer related disease risk). Test-related distress is thought to decrease with time from the disclosure visit. We will summarize test-related distress at each time point, as well as change score. We will examine baseline characteristics to evaluate the potential for bias. In addition to complete case analysis, sensitivity analyses (e.g., using weighted methods) may occur to evaluate bias. We will use clustered Wilcoxon test for mean score comparison between groups at each time point. In addition, mean change in score from T1 to T3 will be modeled using GEE model adjusting for patient characteristics. We will use Autoregressive (AR1) and compound symmetry working correlation matrix to account for repeated measurement correlation and within-physician correlation. The significance of the coefficient will be tested to determine difference between two groups.

General genomic knowledge: We hypothesize that patients in the Return of Results plus Pre-test Education (Arm 3) arm will have better general genomic knowledge than the Return of Results only and Usual Care arms (Arms 1/2). To examine this, we will compare the pre/post test scores between the intervention group (Arm 3) and the control groups (Arms 1/2). The pre/post test scores will be calculated by taking the difference in score between pre/post tests and then comparing the mean differences with an independent T-test between control groups (Arms 1/2) versus the exclusive exposure to the HOPE-Genomics tool educational content (Arm 3). We also hypothesize that Arm 3 will have better knowledge of the difference between germline and somatic testing, as measured in the modified Lung-MAP instrument, which has been adapted and implemented in our survey. We will test this difference as above, testing the mean difference in scores of the modified Lung-MAP instrument across Arms 1 and 2 vs Arm 3.

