Appendix H: Patient Script to Invite Viewing of Tool w/ Results – Either Intervention Arm

Dear [PATIENT NAME],

This is the HOPE-Genomics Team at City of Hope. You may remember speaking with [consenter] about your participation in the HOPE-Genomics study, involving a web-based education tool for patients with genetic testing at City of Hope. Thank you for completing your first two surveys for the study!

At this time, we would like to invite you to log into the tool to view your genetic test results. You may log into the tool by clicking the following link: <https://hopegenomics.coh.org/login>.

Once you have viewed the tool, we will send you a follow-up survey. We have also attached instructions for viewing the tool.

If you have any problems accessing the tool, we can accommodate in-person visits at City of Hope Duarte campus or remote visits using web conferencing (i.e. Zoom). Please call [INSERT CRA'S PHONE NUMBER] or email us at [contact] if you would like to schedule an appointment to speak with study staff.

If you have any additional questions about this research study, please call the Principal Investigator, [name] at [contact] or the Clinical Research Coordinator, [name] at [contact]. You can also reach the Institutional Review Board at City of Hope by calling [contact].

Thank you for all your help with our research at City of Hope, and we look forward to hearing from you!

The HOPE-Genomics Team

[name], [name], [name], [name], and [name]

Division of Clinical Cancer Genomics

Medical Oncology and Therapeutics Research

Department of Population Sciences

City of Hope Comprehensive Cancer Center

[name]

[name]

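### The Arm 3 set-up scripts tie the pre-test knowledge survey to tool viewing, while section 4.3 schedules it about 2-3 days after baseline in every arm

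*Combined protocol and SAP*

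**What the plan says.** Appendix G (letter) and Appendix S (text message) invite Arm 3 patients to open the tool before their results are ready. Both then say: "Once you have viewed the tool, we will send you a follow-up survey". Appendix G thanks the patient for one completed survey. The next script in the sequence, Appendix H, says: "Thank you for completing your first two surveys for the study". The survey promised in Appendices G and S is therefore the second one, the pre-test survey.

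Section 4.3 sets the timing differently: "Approximately 2-3 days after completing the baseline survey, patients in all study arms will complete a pre-test education survey". For paper surveys the rule is also a fixed date: "we will mail the pre-test survey 1 week after mailing the baseline". Neither statement mentions log-in. The same section expects that Arm 3 patients "will view the HOPE-Genomics tool prior to their results disclosure and completion of this survey". For those who have not viewed, its only instruction is that "if patients have not accessed the tool, study staff will encourage and facilitate intervention use". Patients in Arms 1 and 2 see only a pamphlet before this survey.

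Section 6.2.3 compares change in general genomic knowledge by an independent t-test, described as "control groups (Arms 1/2) versus the exclusive exposure to the HOPE-Genomics tool educational content (Arm 3". It gives no analysis set and no rule for a missing survey. Intention-to-treat is stated in section 6.2.2, for Aim 2 only.

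**The concern.** Viewing the tool is a behaviour that occurs after randomisation, and before results only Arm 3 can do it. If the survey waits for viewing, receipt and timing of the outcome measure depend on that behaviour in one arm and on the calendar in the other two. The contrast could then become Arm 3 patients who chose to log in against all patients in Arms 1 and 2, and randomisation would no longer protect it.

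This survey matters more to the hypothesis than the later ones do. Arm 2 gets the educational content once results are in the tool, so the pre-test survey is the only one after baseline that is designed to fall while Arm 3 alone has had it. A pre-test survey missed at this stage cannot be recovered from the 10-day or 3-month surveys.

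**Working it through.** **The passages side by side**

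| Source | What releases the pre-test survey | Depends on viewing? |
|---|---|---|
| Section 4.3, main rule | about 2-3 days after baseline, all arms | no |
| Section 4.3, paper surveys | 1 week after the baseline mailing | no |
| Section 4.3, text reminders | every 96 hours | no |
| Appendix J, survey invitation | follows the first survey; same letter for all arms | no |
| Appendices G and S, Arm 3 only | after the tool has been viewed | yes, as written |

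Section 4.3 expects viewing first and the survey second in Arm 3, but does not say what happens when an Arm 3 patient reaches day 2-3 without viewing. Staff could survey on schedule or wait for viewing. Only the second option treats the arms differently.

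**The plan's own figure.** No power or effect size is given for this comparison. The only power figure is for 10-day recall: 39% against 54%, n = 130 and 260, two-sided alpha 0.05. The pooled proportion is (130 × 0.39 + 260 × 0.54)/390 = 0.49. The standard error is 0.0537 under the null and 0.0528 under the alternative. Then z = (0.15 − 1.96 × 0.0537)/0.0528 = 0.85, which is power of about 80%. It reproduces, but does not bear on this point.

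**Illustration 1: overstatement without selection.** Let p be the share of Arm 3 that does not view (assumed; the documents give none). Suppose non-viewers go unsurveyed and would have gained what controls gain. If the effect in viewers is Δ, the as-randomised effect is (1 − p)Δ, so the viewers-only contrast is larger by 1/(1 − p). Arm 3 has 155 patients (section 6.1).

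| p | Arm 3 patients unsurveyed | Factor |
|---|---|---|
| 0.10 | 155 × 0.10 = 15.5 | 1/0.90 = 1.11 |
| 0.20 | 155 × 0.20 = 31 | 1/0.80 = 1.25 |
| 0.30 | 155 × 0.30 = 46.5 | 1/0.70 = 1.43 |

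At p = 0 the factor is 1.

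**Illustration 2: selection.** Suppose there is no true effect, but viewers and non-viewers differ by d SD in score gain, in either direction. The viewers-only contrast is then biased by p × d in size. Take n = 130 in Arm 3 and 260 in Arms 1/2, which is the analytical sample of 390 split evenly. The standard error is √(1/(130(1 − p)) + 1/260).

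| p | Bias, d = 0.2 to 0.5 SD | Two-sided type I error |
|---|---|---|
| 0.10 | 0.02 to 0.05 SD | 5.4% to 7.3% |
| 0.20 | 0.04 to 0.10 SD | 6.4% to 13.8% |
| 0.30 | 0.06 to 0.15 SD | 7.8% to 23.4% |

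Both p and d are assumptions.

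**Power when everyone is surveyed.** With all 130 and 260 analysed, the standard error is √(1/130 + 1/260) = 0.1074, and the difference detectable with 80% power is (1.96 + 0.84) × 0.1074 = 0.30 SD. If a 0.30 SD effect exists only in viewers, the as-randomised effect is (1 − p) × 0.30. Power is then 71%, 61% and 50% at p = 0.10, 0.20 and 0.30.

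**The case against.** The strongest reply is that the scripts are patient-facing text and do not set procedure. They do not say that the survey is sent only after viewing, and Appendix H uses the same sentence before the 10-day survey, which section 4.5.1 times from release of results in the EHR for all patients. The procedural text points the other way: one schedule for all arms, a fixed mailing date for paper, reminders with no viewing condition, and an arm-neutral invitation letter. Section 6.2.3 names its groups by arm and does not restrict Arm 3 to viewers. All of this stands. It shows that the gate is not an established rule, but it does not settle what staff do with an Arm 3 patient who has not viewed.

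Three stronger readings are tempting, and the documents do not support them:

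- **That the comparison keeps only Arm 3 viewers.** No passage withholds the survey from a non-viewer or drops one from the analysis. Appendix M does say that the study cannot continue without tool access, but it concerns the later step of viewing results.
- **That late Arm 3 viewers are surveyed after results.** Section 4.3 requires "patients in all study arms will complete a pre-test education survey that assesses general genomic knowledge prior to results disclosure". A late survey would depart from that rule, and nothing shows that it happens.
- **That the bias favours the tool.** The outcome is a difference between two scores, so stable differences in literacy are at least partly removed. Well-informed viewers could also gain less because of ceiling effects, which section 6.0 plans to examine.

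The outcome is also exploratory, and section 6.2.3 does not say which surveys supply the pre and post scores (Table 1 lists genomic knowledge at baseline, pre-education, T1 and T2). That limits the consequence. The primary recall outcome and Aim 2 do not use this survey.

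**Conclusion.** The point holds as an unreconciled conflict between Appendices G and S and section 4.3. Read literally, the scripts would make survey receipt and timing in Arm 3 depend on behaviour after randomisation, and section 6.2.3 has no analysis set to guard against that. Whether any Arm 3 patient goes unsurveyed for this reason cannot be told from the documents.

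The size is unknown. The factor of 1.11-1.43 rests on three assumptions: 10-30% non-viewing, every non-viewer unsurveyed, and non-viewers gaining what controls gain. Any further selection bias could go either way. If all Arm 3 patients view, or all are surveyed on schedule whether or not they view, the problem disappears. The change is worth making because it is small and the affected survey cannot be repeated after results are released.

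**What to change.** 1. In Appendices G and S, replace the sentence with one that follows section 4.3, for example: *Your next survey will come on the study schedule, about 2-3 days after your first one (or by mail if you chose paper), whether or not you have viewed the tool.*
2. In section 4.3, state that release of the pre-test survey does not depend on log-in in any arm. Encouragement to view can continue as planned.
3. In section 6.2.3, state that this comparison is by randomised arm and includes Arm 3 patients who did not view. Name the surveys that supply the pre and post scores, and say how a missing survey is handled.

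The cost is one sentence in each of two scripts, short additions to two sections, and a check of how survey release is set up, which the documents do not describe. The statistical price is that the estimated Arm 3 effect and its power fall to the extent that patients do not view, which need not be slight (see the power figures in the working). That is the as-randomised answer. A viewers-only contrast could still be reported beside it if labelled as non-randomised.
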